1. INTRODUCTION

The impact of living with a wound is multifactorial and chronic wounds are associated with a range of morbidities; these wounds and their associated complications can have a significant effect upon a patient's quality of life (QoL) (1, 2). Ineffective wound assessment and management can exacerbate this negative impact upon the patient (3). Wound management strategies should be optimized not only to effectively manage the wound, but also to avoid further wound complications. Frequently reported patient issues associated with chronic wounds include discomfort, pain, malodor, leakage and restriction to daily activities (2).

Whilst dressings are an essential part of wound management, dressing-associated complications can hinder wound healing progression and cause unnecessary distress to the patient. Potential disturbances to the wound can occur as a result of suboptimal dressing choice. There are many potential ways in which a wound dressing, in close contact with the wound bed and surrounding skin, can damage or disturb the wound. These include: sub-optimal moisture balance, adherence, mechanical stress, presence of foreign bodies, sub-optimal temperature, chemical imbalance, and chemical stress (4). Of particular focus in the literature in recent years is the trauma and pain that wound dressing may cause, with the repeated application and removal of dressings that adhere to the wound bed causing trauma and epidermal stripping (5). Frequent application and removal of wound dressings can cause damage to the fragile wound or surrounding skin; this can cause considerable suffering for the patient (4). Ultimately, this trauma to the wound can lead to an increase in wound size, exacerbated pain and delay healing (5).

Pain is an important issue for clinicians to consider when managing chronic wounds. Wound pain can occur from many sources, with wound management procedures (including dressing changes) contributing to this pain (5). When compared to dressings with traditional adhesives, the use of wound dressings incorporating soft silicone can minimize traumatic injuries to the wound/peri-wound skin, as well as minimizing dressing-associated pain (6-8). Research has demonstrated the potential of these atraumatic wound dressings in overcoming these issues.

Whilst optimal dressing choice is important in achieving good healing progression, it is also important to minimize the frequency of dressing changes to enable healing to occur undisturbed (9). Frequent removal and reapplication of wound dressings may delay wound healing through mechanical disturbance to the healing process, temperature loss at the wound site (affecting the cellular healing process) and potential increase in the ingress of harmful bacteria to the wound site (9). Wound healing may be further hindered as a result of psychological stress and pain during dressing changes (9).

A dressing's ability to absorb and retain wound exudate is a key influential factor in terms of dressing wear time (9). Whilst exudate production is a part of the normal wound healing trajectory and an essential component to healing, when excessive exudate is not managed effectively it can have a negative impact on the patient (3). Wound exudate is associated with

Investigation Code **MxBFlex_02** **Final Version** **Approval date** **2018-06-19****Central Amendment 1 Approval date** **2018-11-08****Central Amendment 2 Approval date**

several complications. These include: leakage, maceration, pain and discomfort, malodor, and psychological and psychosocial implications, all of which can impede patient QoL (3, 10-13). Chronic wounds may produce high levels of exudate as a result of a prolonged inflammatory response. Both diabetic foot ulcers (DFUs) and venous leg ulcers (VLUs) are often associated with high levels of wound exudate (14-16).

In terms of exudate management, the ideal wound dressing has several key functions: to optimally handle fluid (absorption and retention of exudate and its components, even under pressure); to reduce the risk of leakage; to reduce the spread of exudate onto the peri-wound area (thus reducing the risk of maceration); and to act as a bacterial barrier. The dressing should also ensure conformability, provide patient comfort, be easy to use, provide optimal dressing change frequency, minimize wound disturbance, and should be cost-effective (14). Previous research has demonstrated the ability of a layered foam dressing with siliconized adhesive to effectively manage wound exudate in exuding wounds, whilst maintaining a moist wound healing environment (6, 8, 17, 18). The adhesion of the dressing to the wound or surrounding skin is a further contributory factor that affects dressing wear time. The ability of the dressing to conform to body contours helps to ensure dressing adhesion (9).

Extended dressing wear may add value not only to the patient, but also to the health care provider. Frequent dressing changes are a huge cost driver and can impact greatly on resources (9). Minimizing the number of dressing changes (depending on the condition of the wound), may help to minimize unnecessary disturbance to the wound, minimize pain and stress for the patient, limit exposure of the wound to contamination and help to limit wound care costs (associated with nursing time, materials, pain medication, and medication for dressing-related trauma).

The aim of this clinical investigation is to evaluate and compare three different foam dressings in the local management of chronic wounds (i.e. VLUs and DFUs) in an outpatient setting. Mepilex® Border Flex will be evaluated versus Optifoam (Medline) and Allevyn Life (Smith&Nephew) within three focus areas; efficacy and safety of the dressings, subject-centric outcomes and health economic evaluation.

2. OBJECTIVES

Primary Objective

To demonstrate superiority in efficacy of Mepilex® Border Flex versus Optifoam Gentle EX and Allevyn Life in the management of venous leg ulcers (VLUs) and diabetic foot ulcers (DFUs) in an outpatient setting, as determined by dressing durability (i.e. wear time).

Secondary Objectives

- To compare clinical wound characteristics during wound management with each of the test dressings (in combination with standard care), including the rate of wound healing, peri-wound skin condition, and local pain levels.

Investigation Code	MxBFlex_02	Final Version	Approval date	2018-06-19
		Central Amendment 1	Approval date	2018-11-08
		Central Amendment 2	Approval date	

- To evaluate the safety of the three test dressings in terms of occurrence of device related adverse events (AEs).
- To study patient-centric outcomes associated with each of the test dressings.

Health Economics Objective

- To retrospectively compare the cost-effectiveness of the three wound dressings.

Primary Endpoint:

Wound dressing durability, as defined as the interval of time to dressing strikethrough and need for dressing change (dressing wear time [days]).

Secondary Endpoints:

- Clinical wound characteristics: wound healing status, condition of surrounding skin, signs of infection, and local pain levels.
- Number of device related (AEs) associated with each of the test dressings.
- Patient-centric outcomes between three treatment groups.

Additional Safety Measures

- The incidence of AEs and SAEs associated with each of the test dressings.

Health Economics Endpoint

To retrospectively compare resource-use as related to:

- Quantity of dressing changes per week (stratified by wound type)
- Time required per dressing change (in minutes)
 - a. Start time: Initiation of old dressing removal
 - b. End time: New dressing is securely in place
- Staff cost associated with dressing change
 - a. Identification of those involved with dressing change (e.g., MD, Nurse, Assistant, etc.)
 - b. Average hourly rate for those individuals directly involved with dressing change
(This can be market data if individuals do not want to provide actual salary information)
- Material Cost
 - a. Quantity of each product (dressing) used per week
 - b. Size of dressings used
 - c. Cost of each dressing used per week

Investigation Code	MxBFlex_02	Final Version	Approval date	2018-06-19
		Central Amendment 1	Approval date	2018-11-08
		Central Amendment 2	Approval date	

- d. Other material cost used in dressing change
 - i. Identification of products used per week
 - ii. Quantity of each product used per week
 - iii. Cost of each product used per week

4. INVESTIGATION PLAN AND PROCEDURES

4.1 Overall Design and Flow Chart

Study Design

Prospective, randomized, controlled clinical trial (RCT) using a 2x2 cross-over (repeated measures) design to evaluate safety and efficacy. The study will be conducted in an outpatient setting of an academic clinical center.

Each subject will be randomly assigned to one of four treatment groups. The treatments and treatment schedule are detailed in the table below:

Table 1. Treatment Groups

	Treatment Group 1	Treatment Group 2	Treatment Group 3	Treatment Group 4
Week 1	Tr. B	Tr. A	Tr. C	Tr. A
Week 2	Tr. B	Tr. A	Tr. C	Tr. A
Week 3	Tr. A	Tr. B	Tr. A	Tr. C
Week 4	Tr. A	Tr. B	Tr. A	Tr. C

*A=Study Product, B=Comparator Product 1, C=Comparator Product 2

Approximately 40 subjects will be enrolled to have 32 subjects for the evaluation. Approximately 50% of the subjects will be in the VLU group and 50% of the subjects in the DFU group. Treatment sequence will be randomized so that a fair distribution is achieved. The total duration of the study will be approximately 4 weeks or 28 ± 2 days.

Visit Schedule

Potential study subjects will be screened for eligibility. Inclusion and exclusion criteria, vital signs, medical record reviews, subject demographics and informed consent will be performed and obtained at the Screening Visit (Day 0). If the patient meets the study eligibility criteria, he or she will be asked to sign consent. Study subjects will be randomized into one of four treatment groups. The test wound dressing will be applied at screening (Day-0) and evaluations will take place twice weekly throughout the Treatment Period. The scheduled dressing change will be on Day 7 of each treatment week (e.g. Visit Days 7, 14, 21 and 28), unless a dressing change is necessary because of strikethrough loss of adherence or discomfort. There will be a total of 8 visits to the Wound Care Center during the Treatment Period. During those visits, evaluations will be performed to assess the condition of the wound dressing, the wound, wound pain and patient comfort.

Investigation Code	MxBFlex_02	Final Version	Approval date	2018-06-19
		Central Amendment 1	Approval date	2018-11-08
		Central Amendment 2	Approval date	

All study evaluations will be performed by a study doctor or nurse during the follow-up visit at the Wound Care Center.

All subjects in the VLU group will receive the same compression therapy and all subjects in the DFU group will receive the same off-loading footwear throughout the entire study period.

Study Methods

- Wound dressings will be evaluated twice weekly by the study doctor or study nurse. All other evaluations will be performed once weekly before dressing change.
- There may be an initial debridement (at the investigator's discretion prior to enrollment).
 - Additional debridement is not allowed.
- Wound dressing wear time and durability will be determined by study doctors' judgement and by photography.
- Exudate absorption and exudate dispersion will be determined clinically and by photodigital planimetry.
- Wound surface area will be measured serially using photo-digital planimetric software.
- Wound and surrounding skin characteristics will be evaluated by the study doctor at dressing change.
- Dressing comfort and subject-centric outcomes will be captured at the end of weeks 2 and 4.
- SF12 will be captured at the initial visit and then bi-weekly
- Local wound pain will be evaluated using the Baker-Wong (Faces) Scale before and after each dressing change.

Investigation Code MxBFlex_02 Final Version Approval date 2018-06-19
Central Amendment 1 Approval date 2018-11-08
Central Amendment 2 Approval date

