4.5 Concomitant Treatments

Standard Static Compression Therapy:

All subjects with VLU will have their affected leg treated with one of two static compression bandage systems:

1. Modified Unna's Boot (Unna's paste bandage plus cohesive bandage)
2. 4-Layer Compression Bandage System

Investigation Code **MxBFlex_02** **Final Version** **Approval date** **2018-06-19**
Central Amendment 1 Approval date **2018-11-08**
Central Amendment 2 Approval date

The Compression bandages are removed and reapplied at each dressing evaluation/change.

Off-Loading Footwear:

All subjects with DFU will have their affected foot treated with the following off-loading footwear:

1. OPTIMA® Diabetic boot with the appropriate insole kit based on subject weight and wound size and make the boot non-removable by using the locking system.

Any additional post-operative medication which is considered necessary for the subject's safety and well-being is permitted. However, topical medication applied to the wound is not allowed. All concomitant medication and relevant treatment must be recorded in the appropriate section of the (CRF).

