4.6.2 Efficacy Measurements and Variables

Primary Endpoint	Outcome variable
The Mepilex® Border Flex versus Optifoam and Allevyn Life dressings.	Interval of time (measured in days) to strikethrough, i.e. loss of edge seal/adherence, leaks, dislodgement.
Secondary Endpoints	Outcome variable
Dressing evaluation	
Unchanged - Dressing looks the same as when put on the wound.
 
Partly Saturated - Dressing is <50% saturated with exudate but remains intact.
 
Mostly Saturated – Dressing is >50% saturated with exudates
 
Strike-through – Dressing is completely saturated and exudates have leaked outside the bandage.

Clinical wound characteristics during wound management with each of the test dressings (in combination with standard care).	
Wound status
 
Type of Wound Drainage (Serous, Sanguineous, Serosanguinous, Purulent)
 
Exudate amount (None, Scant/minimal, Moderate, Heavy)
 
Exudate Absorption (Very Poor/Poor/Good/Very Good/NA)
 
Exudate Dispersion
 
 1. wound exudate dispersed 1-25% of pad 2. wound exudate dispersed 26-50% of pad 3. wound exudate dispersed 51-75% of pad 4. wound exudate dispersed 76-100% 5. Is wound dressing completely saturated with no strike through

Investigation Code **MxBFlex_02** Final Version Approval date **2018-06-19**
Central Amendment 1 Approval date **2018-11-08**
Central Amendment 2 Approval date

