The Safety population include all subjects that have at least one application of the Mepilex® Border dressing or at least one of the other study dressings.

Investigation Code	MxBFlex_02	Final Version	Approval date	2018-06-19
		Central Amendment 1	Approval date	2018-11-08
		Central Amendment 2	Approval date	

The distribution of continuous variables and change in continuous variables will be given as mean, standard deviation, median, minimum and maximum and the distribution of categorical and dichotomous variables will be given as numbers and percentages.

All statistical tests will be two-sided and conducted at the 5% significance level.

A baseline table will be given for all included subjects with the distribution of demographics and baseline variables.

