4.8.3 Determination of Sample Size

The expected mean differences in days to strikethrough between the differences Period 1-Period 2 between the two groups Mepilex® Border Flex and active control will be two times the difference in the effect Mepilex® Border Flex minus active control.

We estimate (assume) the SD for the difference in time to strikethrough between Period 2 and Period 1 to be 0.65 days both in the group started with Mepilex® Border Flex and in the group started with active control.

In order to find a difference in one half day between days to strikethrough between Mepilex® Border Flex and active control with a power of 80% a total of 16 evaluable subjects is needed.

This implies that in the first cross-over study 16 subjects will be randomized to the sequence Mepilex® Border Flex in the first period and Optifoam in the second period and to the sequence Optifoam in the first period and Mepilex® Border Flex in the second period in proportions 1:1.

In the second cross-over study 16 subjects will be randomized to the sequence Mepilex® Border Flex in the first period and Allevyn Life in the second period and to the sequence Allevyn Life in the first period and Mepilex® Border Flex in the second period in proportions 1:1. Both

Investigation Code	MxBFlex_02	Final Version	Approval date	2018-06-19
		Central Amendment 1	Approval date	2018-11-08
		Central Amendment 2	Approval date	

the randomizations above will be stratified by diagnosis Venous Leg Ulcer / Diabetic Foot Ulcer.

A total of 32 subjects will be included in the two cross-over studies.

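### Strikethrough is assessed at scheduled visits 3–4 days apart with no rule for dating failures in between, so the SD of 0.65 day and the 80% power for half a day are unsupported for the recorded variable

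*Combined protocol and SAP*

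**What the plan says.** Section 4.6.2 defines the primary outcome as "Interval of time (measured in days) to strikethrough, i.e. loss of edge seal/adherence, leaks, dislodgement". On assessment, section 4.1 says "Wound dressings will be evaluated twice weekly by the study doctor or study nurse", places all study evaluations at the clinic visit, and rests wear time on the study doctor's judgement and photography. Table 2 lists visits at Days 3, 7, 10, 14, 17, 21, 24 and 28, each -1/+2 days.

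Between visits the dressing is covered. Under section 4.5, venous ulcers are under compression bandages that come off at each evaluation or change, and for diabetic foot ulcers staff are to "make the boot non-removable by using the locking system".

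There are routes to earlier detection. The synopsis allows changes as needed, section 4.1 allows them for strikethrough, loss of adherence or discomfort, and the notes to Table 2 say that an unscheduled visit records wound status and dressing change.

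The sample size (section 4.8.3) is set "In order to find a difference in one half day between days to strikethrough" between dressings; "with a power of 80% a total of 16 evaluable subjects is needed". It assumes the "SD for the difference in time to strikethrough between Period 2 and Period 1 to be 0.65 days", with no source and no mention of the visit grid. Sections 4.8.1 and 4.8.2 contain no rule for dating a failure found at a visit and no interval-censored analysis.

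**The concern.** The target difference is half a day, while the scheduled checks are 3 or 4 days apart. If a failure takes the date of the visit at which it is found, failures at 3.5 and at 6.5 days after application both count as Day 7. A true half-day advantage is then recorded either as nothing or as a jump of several days.

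The windows add to this. Table 2 numbers its days from Day 0, and nothing asks for a subject's visits to fall on the same days in both periods. The primary analysis uses the within-subject difference between periods, so unequal visit timing enters it directly. No blinding is described and the dressings carry standard product labelling, so a difference in visit timing between dressings cannot be ruled out.

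At stake is the stated power for the only primary endpoint, in each of two comparisons with 16 subjects.

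**Working it through.** **1. The plan's own figure.** From section 4.8.3: difference 0.5 day; SD of the Period 2 minus Period 1 difference 0.65; 16 subjects, 8 per sequence. From section 4.8.1: "All statistical tests will be two-sided and conducted at the 5% significance level". The contrast between sequence groups "will be two times the difference in the effect", so it is 2 × 0.5 = 1.0 day. By the noncentral t distribution, 8 per sequence gives power 0.816 and 7 per sequence gives 0.753. The stated 16 is confirmed.

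**2. How power depends on the SD** (8 per sequence, contrast 1.0 day):

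| SD of recorded period difference | Power |
|---|---|
| 0.65 | 0.82 |
| 0.80 | 0.64 |
| 1.00 | 0.46 |
| 1.25 | 0.32 |
| 1.50 | 0.24 |

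**3. Dating to the calendar day.** If 0.65 is the SD of exact times, rounding each of the two times to a whole day adds a variance of about 1/12 each: SD = √(0.65² + 2/12) = √0.589 = 0.77. Power is then 0.68, and 22 subjects would be needed for 80%. If 0.65 already describes day-dated records, power stays at 0.82.

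**4. Dating at scheduled visits.** The planned permutation test was simulated over all 12,870 splits of 8 against 8, with 600–1,000 trials per scenario. The true difference was 0.5 day and the SD of the true period difference 0.65. Each failure was dated at the first visit at or after it. Assumptions that are not in the documents: control mean wear 2.0–5.5 days, between-subject SD 0–1.5 days, 1–3 dressings averaged per period. Visits fell on Days 3 and 7 exactly, or were spread evenly over their windows (Days 2–5 and 6–9).

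Power with one dressing per period and between-subject SD 0.5:

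| Control mean (days) | Exact time | Calendar day | Visits on Days 3 and 7 | Visits across windows |
|---|---|---|---|---|
| 2.0 | 0.84 | 0.54 | 0.06 | 0.09 |
| 2.75 | 0.80 | 0.55 | 0.27 | 0.10 |
| 3.5 | 0.82 | 0.53 | 0.03 | 0.08 |
| 4.75 | 0.81 | 0.56 | 0.00 | 0.07 |
| 5.5 | 0.79 | 0.49 | 0.00 | 0.03 |

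Over all scenarios the ranges were 0.77–0.84 (exact), 0.30–0.71 (calendar day), 0.00–0.53 (fixed visits) and 0.03–0.26 (windows). A further run, in which a dressing that fails early is replaced and all dressings in the 14-day period are averaged, gave 0–0.61. No visit-dated scenario reached 0.80.

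The recorded effect is distorted in both directions. On fixed visits it was as high as 1.65 days when the control mean lay just below Day 3. When it lay at 4.75–5.5 days, the recorded effect was 0.00–0.28 day with either visit pattern.

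**5. The windows.** The gap from the Day 3 to the Day 7 visit can be 6 − 5 = 1 to 9 − 2 = 7 days. From Day 7 to Day 10 it can be 9 − 9 = 0 to 12 − 6 = 6 days. A single dressing can meet its weekly visit after 13 − 9 = 4 days or 16 − 6 = 10 days. For two weekly dressings averaged per period the effect is smaller. With Day 14 held on Day 16 and Day 28 on Day 27, the means are 16/2 = 8 and (27 − 16)/2 = 5.5 days, a shift of 2.5 days, which is still five times the target difference.

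**The case against.** The best reply is that failures need not wait for a scheduled visit. Changes are allowed when needed, unscheduled visits are recorded, and section 4.6.2 describes strike-through as exudate escaping the bandage, which a subject may well notice. This stands, and it rules out saying that failures are dated only at scheduled visits. It is a partial remedy. No passage tells subjects to attend at failure or makes such a visit the failure date, and edge lift under a bandage or in a locked boot may go unseen.

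A reader might go further and infer that the design cannot resolve half a day at all. The documents do not support that: with prompt day-level dating, power lies between about 0.3 and 0.82.

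A reader might also infer that an SD of 0.65 is impossible. If every time were recorded as 3 or 7 days, differences would be −4, 0 or +4. A mean of 0.5 then needs a variance of at least 16 × 0.125 − 0.25 = 1.75, an SD of 1.32. That bound fails once replacement dressings are averaged. Over 14 days the possible means are 14/2 = 7, 14/3 = 4.67 and 14/4 = 3.5. Between the last two, the step is 7/6 day and the minimum SD is √(0.5 × 7/6 − 0.25) = 0.58, below 0.65. It also fails when visits spread over their windows. The plan does not say how dressings within a period are combined, so neither bound is established.

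Two further cautions stand. Counting windows from Day 0 is read from the numbering in Table 2 and is not a stated rule. The case report form template (Appendix C) is not in the text available, so it may hold date fields that cannot be seen here.

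**Conclusion.** The point holds in this form: the sample size arithmetic is right, but the SD of 0.65 day, and with it the 80% power for half a day, is not supported for the variable as it will be recorded. With 16 subjects, power is about 0–60% if failures are dated at scheduled visits, about 68% (t-based) if every one is dated to the calendar day, and 82% only if 0.65 is already the SD of day-dated records. The truth depends on how many failures prompt an early visit, which the plan does not address. The simulated figures rest on assumed wear times (control mean about 2 to 6 days, between-subject SD 0–1.5 days). The consistent result is that no visit-dated scenario reached 80%.

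**What to change.** 1. **Section 4.8.3.** Restate the power for half a day with an SD that fits the recorded variable, visit-dated or day-dated, and give its source; otherwise withdraw the 80% claim. Cost: a less favourable figure in the text. No patients need to be added.
2. **Table 2.** Ask that each subject's evaluation visits fall on matching days in Period 1 and Period 2, as far as the existing windows allow. Cost: less freedom in booking. The match will not always be exact once dressings fail on different days. This concerns the booking of evaluations only, not the criteria for changing a dressing.
3. **eCRF and sections 4.8.1–4.8.2.** For each dressing, record the application date, the last visit at which it was intact, and the date failure was first noticed or found. State one rule that turns these into the primary value, and add an interval-censored sensitivity analysis. Cost: a few date fields and one extra analysis, with no extra visits.

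The primary endpoint should stay as days to strikethrough. Replacing it with a three-level visit score would discard the dates that item 3 collects, and simulated power for such a score was only 0–26%, against 49–58% for calendar-day dating in the same model.
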